# 2.4.5.3 Subject Withdrawals

Subjects may leave the study at their own discretion at any time. Experts from the gastrointestinal or anorectal department in each site may also decide, for the sake of participants' health, to discontinue participation (due to worsening of symptoms, or the occurrence of a serious adverse event).

## 2.4.6 Interventions

# 2.4.6.1 Acupuncturists and Apparatus

Acupuncturists in each site need to have an official license and at least two-year clinical experience. Before

conducting the trial, acupuncturists will be trained by principle investigator.

Huatuo disposable needles (size 0.30 mm×40mm, 0.30 mm×50mm, 0.30mm×75mm, Suzhou Medical Appliance, Suzhou, Jiangsu Province, China), and Huatuo electro-acupuncture apparatus (type SDZ-V, Suzhou Medical Appliance, Suzhou, Jiangsu Province, China) will be used.

## 2.4.6.2 Electro-acupuncture Group

# Acupoints:

Bilateral Tianshu (ST 25), Fujie (SP 14), Shangjuxu (ST 37) will be used in all participants. Additionally, BL33, DU20 and DU24 could be used according to the individual situation: BL33 could be used for severe straining if any, DU20 and DU24 could be used for participants accompanied with the symptoms of anxiety and depression.

According to the WHO Standardized Acupuncture Points Location 14.

### Manipulation:

After sterilizing the skin in supine position, needles with the size of 0.30mm×50mm, or 0.35mm×75mm will be inserted into ST25 and SP14 slowly and vertically, without manipulation, for approximately 30-70mm until they pierce into the muscle layer of the abdominal wall. Needles with the size of 0.30mm×40mm will be inserted into ST37 vertically for about 25mm. If BL33 is needed, all points could be simultaneously needled when participants are in the lateral decubitus position. The needle is inserted at BL33 inwardly and downwardly at an angle of 30-45 degree to a depth of 50–60mm. For DU20 and DU24, the needle is obliquely inserted backwards into the galea aponeurotica to a depth of 40mm.

Paired alligator clips of the EA apparatus will be attached transversely to the needle holders of bilateral ST25 and SP14 (and BL33 if needed). EA stimulation will last for 30 minutes with a dilatational wave of 10/50 Hz and current intensity of 0.5-2.0mA. The skin around the acupoints shivering mildly indicates the proper dose. For ST37 (and DU20, DU24 if needed), three small equal manipulations of twirling, lifting and thrusting will be performed. The participants' feeling of soreness and/or distention indicates the proper manipulation of deqi. The twirling, lifting and thrusting manipulation should be performed every 10 minutes, three times, in 30 minutes. Course of treatment:

Each participant will accept an 8-continuous-week treatment with 28 sessions in total. The participants will be treated 30 minutes for each session, once a day, five times per week in the first two weeks, and three times per week in the latter 6 weeks.

### 2.4.6.3 Prucalopride Group

Participants will take Prucalopride Succinate (Janssen S.P.A) orally at a dose of 2 mg/day before breakfast for 8 weeks. Participants will undergo an electrocardiogram (ECG) at the 8th week, and the drug will be taken for another 24 weeks if no QT interval elongation or other severe cardiac adverse events (like myocardial infarction, severe arrhythmia, etc.). The use of other medicine for constipation will not be allowed during the trial. Prucalopride will be distributed to the participants beforehand every 2 weeks in the treatment period, and every 4 weeks in the follow-up period. The untaken pills will be recycled on the day of next distribution.

## 2.4.6.4 Rescue Medicine

Bisacodyl (5–10 mg) and glycerin enema (110 ml) can be used for participants who fail to have a bowel movement for 3 or more consecutive days. Furthermore, the date, specific time, dose of bisacodyl or glycerin enema use should be recorded in the stool diary and case report form (CRF).

Other drugs or measurements for constipation are not allowed; however, if used, details of the date, specific time, dose should also be recorded in the stool diary and CRF. Rescue medicine is available during the whole study period (baseline assessment [run-in], treatment, and follow-up); nevertheless, it is not allowed 48 hours before and after the first treatment, no matter EA or prucalopride, in order to evaluate the time to the first spontaneous defecation. Rescue medicine will be distributed to the participants beforehand every 2 weeks in the treatment period, and every 4 weeks in the follow-up period.

# 2.4.6.5 Research Period

The whole research period is 34 weeks, including 2-week baseline assessment (run-in) period (week -2, week -1), 8-week treatment period (weeks 1–8), and 24-week follow-up period (weeks 9–32). The time frame of the trial is presented in Figure 1.

Outcome assessing points: 1) baseline assessment (run-in) period: the last day of week -2 and week -1 (baseline evaluation); at week 0, the randomization and the first treatment will be carried out in one day. 2) Treatment period: the last day of week 2, week 4, week 6, week 8. 3) Follow-up period: the last day of week 12, week 16, week 20, week 32.

[figure not shown]

FIGURE 1 RESEARCH PERIOD AND ASSESSING POINTS

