### 2.4.7 Subject Evaluations and Outcomes

### 2.4.7.1 Baseline Evaluations

Outcomes contain the complete spontaneous bowel movements (CSBMs), spontaneous bowel movements (SBMs), stool consistency (according to Bristol Stool Scale), straining during defecation, rescue medicine used, and the form of Chinese-version Patient Assessment of Constipation Quality of Life (PAC-QOL). Participants will record their bowel movements, constipation-related symptoms, medicine used for constipation every day during week -2, week -1, weeks 1-8, weeks 11-12, weeks 15-16, weeks 19-20, and weeks 31-32. In both groups, participants without bowel movements (BMs) for 3 or more consecutive days were allowed to use oral bisacodyl (5-10mg a day before bedtime, Boehringer Ingelheim) or 110 ml glycerol enema as rescue medicine with documentation (time, dosage, and frequency of use) in the stool diary.

The SBMs are the bowel movements that occur in the absence of rescue medicine, or other assistant methods (laxatives, enemas, suppositories usage, or digging out by fingers) within the preceding 24 hours. When participants used rescue medicine, or other measures for constipation, the defecation within 24 hours was considered a non-spontaneous bowel movement, whereas defecation exceeding 24 hours was deemed an SBM. CSBMs were the SBMs with the sensation of complete evacuation.

Outcome record time point: Baseline (week 0), week 2, week 4, week 6, week 8, week 12, week 16, week 20, and week 32 (Figure 1).

Outcome assessing time frame: baseline period (weeks -2 to week -1), the first 2 weeks of treatment (weeks 1-2), the latter 6 weeks of treatment (weeks 3-8), and the follow-up periods (weeks 11-12, weeks 15-16, weeks 19-20, weeks 31-32).

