# 2.4.8 Safety Assessment

## 2.4.8.1 Adverse Events

The adverse events are some unintended symptoms, physical signs, or health conditions that show up during the whole trial. They may or may not have causality with the interventions. A health condition or an illness existing before the trial can be deemed as an adverse event (AE) if the situation becomes worse within the study period. An abnormal result of the laboratory examination can be deemed as an AE only if it causes some clinical symptoms and/or require related treatments. We will look for adverse events by asking the participants non-inducing questions at each assessing point. We will also look for the adverse events through participants' self-report, or through physical examination, or by laboratory examination. All the adverse events must be recorded at length on the CRF. If an AE was observed, the following information should be acquired:

- 1. Degree of severity (mild, moderate, severe);
- 2. If it is related to the interventions (affirmably, very likely, possibly, possibly not, affirmably not);
- 3. Duration of the AE (start and end dates, whether still exists at the end of the trial);
- 4. Severe adverse effect (SAE) or not.

SAE is defined as any of the following:

- 1. Fatal or life threatening;
- 2. Permanent or loss of function or disability;
- 3. Need hospitalization or need prolonged hospitalization;
- 4. Severe medical accidents, which need medical or surgical interventions to prevent any of the above occurs.

Solution for controlling the adverse events:

Observation, without any treatment;

Adjusting or stopping the treatment;

Aborting the trial permanently;

Adding combined drugs therapy;

Giving non-pharmacologic therapy;

Hospitalizing or prolonging hospitalization.

All the treatment measures for the adverse events should be recorded in detail on the CRF. We will follow up with the adverse event through the whole trial until its resolution. We will confirm if it is permanent. At every assessing point, we will evaluate the adverse event's severity, relation to our interventions, and arrange appropriate the treatments. The common adverse events related to the interventions are listed in the investigator's brochure. To update the brochure, related adverse events will be announced by the form of investigator's note (IN). We will also discuss with the participants about the adverse events that might occur during the trial.

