# 2.4.8.3 Safety and Acceptance Evaluation

The adverse events should be documented in detail over the treatment and follow-up periods. Participants and

acupuncturists will be responsible for recording adverse events.

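### Scheduled adverse event questioning stops for 12 weeks (end of week 20 to end of week 32) while daily prucalopride continues, so late non-serious events rest on spontaneous report or long recall

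*Supplement*

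**What the plan says.** **When participants are asked.** Final protocol 2.4.8.1 states: "We will look for adverse events by asking the participants non-inducing questions at each assessing point". SAP 11.1 says the same in substance. Section 2.4.8.1 also places the evaluation of each event's severity and relation to the interventions at every assessing point.

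**When the assessing points fall.** Section 2.4.6.5 gives "Treatment period: the last day of week 2, week 4, week 6, week 8" and then "Follow-up period: the last day of week 12, week 16, week 20, week 32". Section 2.4.7.1 agrees: "Outcome record time point: Baseline (week 0), week 2, week 4, week 6, week 8, week 12, week 16, week 20, and week 32". SAP 8 and SAP 10.1 list the same post-baseline weeks.

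**What else captures events.** Section 2.4.8.1 continues: "We will also look for the adverse events through participants' self-report, or through physical examination, or by laboratory examination". It also requires known events to be followed through the trial until they resolve. Section 2.4.8.2 requires any serious event, related or not, to be reported within 24 hours, from consent to 30 days after the study ends. Section 2.4.8.3 adds: "The adverse events should be documented in detail over the treatment and follow-up periods", and makes participants and acupuncturists responsible for recording.

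**Contacts during follow-up.** Section 2.4.6.3: "Prucalopride will be distributed to the participants beforehand every 2 weeks in the treatment period, and every 4 weeks in the follow-up period". Section 2.4.6.4, without restriction by arm: "Rescue medicine will be distributed to the participants beforehand every 2 weeks in the treatment period, and every 4 weeks in the follow-up period". Under 2.4.9, prucalopride tablets are returned every four weeks in follow-up and the counts entered in the CRF. No section links an adverse event question to these contacts.

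**Analysis.** SAP 13.7 compares the proportion of participants with adverse events between groups by chi-squared or Fisher's exact test.

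**The concern.** The assessing points follow the diary blocks used for efficacy (weeks 11-12, 15-16, 19-20 and 31-32). Tying adverse event questioning to them carries the efficacy spacing into safety ascertainment. That does no harm while the points are 2 or 4 weeks apart. It matters in the last interval, when one arm is still taking its study treatment every day and the other finished at week 8.

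The other routes have no timetable in that interval. The text schedules no physical or laboratory examination there. The follow-up diary items listed in 2.4.7.4 include no adverse event entry, and no diary covers weeks 21-30. A mild or moderate event in week 22 is therefore recorded only if the participant volunteers it or still remembers it at week 32. At stake are the completeness and dating of late non-serious events, and so the comparison in SAP 13.7.

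**Working it through.** **Inputs.** Assessing points: weeks 2, 4, 6, 8, 12, 16, 20, 32 (2.4.6.5, 2.4.7.1). Prucalopride: daily for 8 weeks, then 24 more if the stated cardiac condition is met (2.4.6.3). Supply in follow-up: every 4 weeks (2.4.6.3, 2.4.6.4). Per-protocol threshold for the drug arm: 180 days (2.4.7-independent; section 7.2 and SAP 13.2).

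**Check of the plan's own figure.** 2 + 8 + 24 = 34 weeks in all, and weeks 9 to 32 inclusive are 24 weeks. Both agree with 2.4.6.5.

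**Intervals between questions** (each point minus the one before, from week 0):

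| From – to (week) | 0–2 | 2–4 | 4–6 | 6–8 | 8–12 | 12–16 | 16–20 | 20–32 |
|---|---|---|---|---|---|---|---|---|
| Weeks | 2 | 2 | 2 | 2 | 4 | 4 | 4 | 12 |

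The last interval is 12/4 = 3 times the earlier follow-up interval and 12/2 = 6 times the treatment-period interval.

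**Share of prucalopride dosing in the gap.**
- Gap: 12 × 7 = 84 days.
- Follow-up dosing: 24 × 7 = 168 days; 84/168 = 50%.
- All planned dosing: 32 × 7 = 224 days; 84/224 = 37.5%.

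**Is the gap incidental to the analysed population?** By the end of week 20 at most 20 × 7 = 140 doses can have been taken. The per-protocol set needs 180 days of drug, so each prucalopride participant in it takes at least 180 − 140 = 40 doses within the gap.

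**Contacts already planned.** If the first follow-up supply is at the end of week 8 (an assumption), 4-weekly supplies fall at weeks 8, 12, 16, 20, 24 and 28. Weeks 24 and 28 are the two that are not assessing points. Questions there would split the 12-week interval into three of 4 weeks.

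**Effect on SAP 13.7.** The measure is per participant. An unrecorded late event changes the proportion only if that participant has no other recorded event. The documents give no adverse event rates, so the bias cannot be put as a number.

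**The case against.** The strongest reply is that the protocol does not depend on scheduled questions alone. Self-report is named, participants share responsibility for recording through follow-up, serious events must be reported within 24 hours, and the week-32 question looks back over the whole gap. The questioning schedule is the same in both arms. Section 2.3 speaks of the safety and acceptance of EA, which ends at week 8. Any under-count of late prucalopride events would flatter the comparator, not EA. All of this stands. It confines the point to non-serious events and their dating, but does not close the gap. Section 2.2 also gives comparison of efficacy and safety as an aim, and SAP 13.7 tests the difference.

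Three stronger readings are tempting and should not be made:

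- *That events in the gap are never asked about.* The week-32 question covers them by recall, and the other routes remain open.
- *That an event open at week 20 is left for 12 weeks.* Section 2.4.8.1 requires follow-up until resolution; only the formal re-grading is tied to assessing points.
- *That the cardiac condition for continuing prucalopride goes unchecked.* In 2.4.6.3 it stands beside the week-8 ECG and reads most naturally as a gate at that time. A severe cardiac event would usually be serious and so reportable within 24 hours.

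It is also fair to say that the documents do not state that supply contacts are face to face, and that Figure 1 and the CRF, which could not be read here, might hold further adverse event prompts. The written schedule is nevertheless explicit and the same in protocol and SAP.

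**Conclusion.** The point holds as a limited weakness in data collection. For 12 weeks, half of follow-up dosing and 37.5% of all planned prucalopride dosing, non-serious events rest on spontaneous report or on recall up to three times longer than earlier in follow-up. Late events can be under-recorded, mainly in the arm still on treatment, which would tend to lower the prucalopride proportion in SAP 13.7. The size of that effect is unknown. Reporting of serious events, follow-up of known events and the primary outcome (weeks 3-8) are not affected.

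This rests on three assumptions: that the written list of assessing points is complete, that no adverse event prompt is attached to supply contacts elsewhere, and that participants continue prucalopride to week 32 as planned.

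**What to change.** In protocol 2.4.8.1 and SAP 11.1, require the same non-leading adverse event question, and an update of open events, at each 4-weekly supply contact in follow-up, in both arms. This adds about weeks 24 and 28. Where supply is not face to face, use phone or message, routes the protocol already uses for follow-up (2.4.7.4, 5.3). Leave the efficacy assessing points as they are. No treatment rule or clinical test changes.

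The cost is a wording change and two short CRF entries per participant, at most 560 × 2 = 1,120 entries at the planned sample size. A few more mild events will be recorded. The gain is that the longest recall interval falls from 12 to 4 weeks, equally in both arms.

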### 2.4.7 Subject Evaluations and Outcomes

### 2.4.7.1 Baseline Evaluations

Outcomes contain the complete spontaneous bowel movements (CSBMs), spontaneous bowel movements (SBMs), stool consistency (according to Bristol Stool Scale), straining during defecation, rescue medicine used, and the form of Chinese-version Patient Assessment of Constipation Quality of Life (PAC-QOL). Participants will record their bowel movements, constipation-related symptoms, medicine used for constipation every day during week -2, week -1, weeks 1-8, weeks 11-12, weeks 15-16, weeks 19-20, and weeks 31-32. In both groups, participants without bowel movements (BMs) for 3 or more consecutive days were allowed to use oral bisacodyl (5-10mg a day before bedtime, Boehringer Ingelheim) or 110 ml glycerol enema as rescue medicine with documentation (time, dosage, and frequency of use) in the stool diary.

The SBMs are the bowel movements that occur in the absence of rescue medicine, or other assistant methods (laxatives, enemas, suppositories usage, or digging out by fingers) within the preceding 24 hours. When participants used rescue medicine, or other measures for constipation, the defecation within 24 hours was considered a non-spontaneous bowel movement, whereas defecation exceeding 24 hours was deemed an SBM. CSBMs were the SBMs with the sensation of complete evacuation.

Outcome record time point: Baseline (week 0), week 2, week 4, week 6, week 8, week 12, week 16, week 20, and week 32 (Figure 1).

Outcome assessing time frame: baseline period (weeks -2 to week -1), the first 2 weeks of treatment (weeks 1-2), the latter 6 weeks of treatment (weeks 3-8), and the follow-up periods (weeks 11-12, weeks 15-16, weeks 19-20, weeks 31-32).

### 2.4.7.2 Primary Outcome

The primary outcome is the proportion of participants with 3 or more mean weekly CSBMs over weeks 3–8. Assessing time frame: the latter 6 weeks of treatment (weeks 3-8).

## 2.4.7.3 Secondary Outcomes

- 1) The proportion of participants with 3 or more mean weekly CSBMs over weeks 1-2, 11-12, 15-16, 19-20, 31-32. EA was discontinued after 8 weeks of treatment, while participants in the prucalopride group continues to take prucalopride for 24 weeks if no QT interval elongation or other severe cardiac adverse events (like myocardial infarction, severe arrhythmia, etc.). Assessing time frame: weeks1-2, weeks 11-12, 15-16, 19-20, 31-32.
- 2) The proportion of participants with  $\geq 1$  increase of mean weekly CSBMs from baseline over weeks 1-2, 3-8, 11-12, 15-16, 19-20, 31-32. Assessing time frame: baseline, weeks 1-2, weeks 3-8, weeks 11-12, 15-16, 19-20, 31-32.
- 3) The change from baseline in mean weekly CSBMs over weeks 1-2, 3-8, 11-12, 15-16, 19-20, 31-32. Assessing time frame: baseline, weeks 1-2, weeks 3-8, weeks 11-12, 15-16, 19-20, 31-32.
- 4) The change from baseline in mean weekly SBMs over weeks 1-2, 3-8, 11-12, 15-16, 19-20, 31-32. Assessing time: baseline, weeks 1-2, weeks 3-8, weeks 11-12, 15-16, 19-20, 31-32.
- 5) The change from baseline in the mean score of stool consistency of each SBM over weeks 1-2 and weeks 3-8. Assessing time: baseline, weeks 1-2 and weeks 3-8. Participants will self-report their stool consistency of each SBM according to the 7-type BSFS (scored by 1 to 7 respectively).

- Type 1: Separate hard lumps, like nuts (hard to pass)
- Type 2: Sausage-shaped, but lumpy
- Type 3: Like a sausage but with cracks on its surface
- Type 4: Like a sausage or snake, smooth and soft
- Type 5: Soft blobs with clear cut edges (passed easily)
- Type 6: Fluffy pieces with ragged edges, a mushy stool
- Type 7: Watery, no solid pieces. Entirely liquid

- 6) The change from baseline in the mean score of straining of each SBM over weeks 1-2, weeks 3-8, weeks 11-12, 15-16, 19-20, 31-32. Assessing time: baseline, weeks 1-2, 3-8, 11-12, 15-16, 19-20, 31-32. Participants will self-report their straining degree of each SBM in the defecation diaries according to the following scale.
  - 0 = not difficult;
  - 1 = a little difficult, need some straining to defecate;
  - 2 = difficult, need straining to defecate;
  - 3 = very difficult, need hard straining to defecate.
- 7) Time to the first CSBMs, which was the time from the first treatment to the first CSBMs counting by days. Rescue medicines are not allowed to be used during 48 hours before and after the first treatment. If the first CSBM had not occurred yet, and rescue medicines were used in the condition of no BM in a succession of three or more days, the BM occurs within 24 hours after the use of rescue medicine will not be regarded as CSBM, and the days-counting will continue till the occur of the first CSBM.
- 8) The change from baseline in the score of PAC-QOL at week 4 and week 8. PAC-QOL is a self-report questionnaire to evaluate the quality of life in participants with constipation, which was distributed by Mapi Research Trust in France. This questionnaire contains 28 items including 4 basic parts of physical discomfort, worries and concerns, psychosocial discomfort, and satisfaction. We use the Chinese version in our trial. Assessing point: baseline, week 4 and week 8.
- 9) The proportion of participants using rescue medicine (bisacodyl or glycerol enema) and the mean weekly dosage of rescue medicine used ((bisacodyl or glycerol enema) over weeks 1-2, 3-8, 11-12, 15-16, 19-20, 31-32. Assessing time frame: baseline, weeks 1-2, 3-8, 11-12, 15-16, 19-20, 31-32.

# 2.4.7.4 Defecation Diaries

## Defecation diaries during the treatment period (week 1 - week 8):

Participants will record their bowel movements (BMs), spontaneous defecation or not, complete evacuation or not, stool consistency, degree of straining, the time, dosage, and frequency of rescue medicine or other assistant methods used every day from the baseline to the end of week 8. Distribution of the defecation diaries: the diary of week 1 will be distributed at the first treatment of week 2 will be distributed at the last treatment of week 1, and the first treatment of week 2, and the diary of week 3 will be distributed at the last treatment of week 2; and so on. The diary of weeks 11-12 (follow-up period) will be distributed at the last treatment of week 8.

